5.2.4 Speech Perception (Endpoint Testing)

All speech perception tests will be conducted with recorded materials in a unilateral, implant-only configuration using the subject's Everyday program. The following endpoint speech perception tests will be performed at Cochlear Americas' Research & Technology Labs or at the Clinical Site. The clinician who conducts endpoint speech testing will not be the same clinician who conducts programming for an individual subject, and the testing clinician will be blinded from the subject's group assignment. Thus, the endpoint speech testing will be double-blinded.

5.2.4.1 Monosyllabic Word Recognition

Monosyllabic word recognition will be conducted using CNC words (Peterson & Lehiste, 1962). The test will be performed in the sound field at 0° azimuth at a level of 60 dBA. Two paired 50-word lists will be administered at each evaluation session, for a total of 100 words. The order of lists will be counterbalanced.

5.2.4.2 Sentence Recognition in Four-Talker Babble

The first speech-in-noise task will be conducted using BKB sentences with a male target talker (Bench et al., 1979). A four-talker babble background will be presented. The level of the babble will be adapted to find the SRT, defined as the SNR in dB providing 50% intelligibility. Sentences will be presented at 65 dBA at 0° azimuth in the sound field, with babble presented from the same spatial location (S0N0). The order of lists will be counterbalanced.

5.2.4.3 Sentence Recognition in Speech-Shaped Noise

A second speech-in-noise test will be completed using untested BKB sentences with a speech-shaped noise background. Sentences will be presented at 65 dBA at 0° azimuth in the sound field, with the competing noise presented from the same spatial location (S0N0). The competing noise will be adapted to find the SRT as described previously. The order of lists will be counterbalanced.

5.2.5 Reading Span Test

The Reading Span Test is a working memory task that measures the ability to simultaneously store and process information (Daneman & Carpenter, 1980). Subjects will be asked to read a sequence of sentences and judge whether each sentence is sense or nonsense. At the end of the sequence, the subject's task is to recall the first word or the last word of each of the preceding sentences.

CONFIDENTIAL

5.2.6 Battery Life Questionnaire

Subjects will be asked to complete two battery questionnaires, one for FAST and one for ACE. Each questionnaire will contain four logs. Subjects will start each battery log with a fully charged battery. Subjects will track what time the processor was turned on with a fully charged battery and what time the processor was turned off (or, if the battery ran out of power, what time this occurred). They will complete this process until they have gone through four cycles of fully charged batteries.

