1.4.2 Secondary Efficacy Objectives

1.4.2.1 *Battery Life*

The secondary efficacy endpoint for battery life will be based on battery logs as recorded by the subject during the take-home period with each strategy. The objective of this secondary endpoint is to demonstrate superiority of FAST compared to ACE for battery life. Success for this secondary endpoint will be based on rejection of the null hypothesis that battery life with FAST is less than or equal to battery life with ACE. The estimated within-subject mean difference in battery life between FAST and ACE will be reported with a 95% confidence interval. A one-sided t-test will be conducted at the 0.025 significance level. The secondary endpoint for difference in battery life is represented by the following hypotheses:

$$H_0: BLD \leq 0,$$

$$H_a: BLD > 0,$$

where:

BLD = within-subject battery life difference for FAST – ACE.

1.4.2.2 *Speech, Spatial, and Qualities of Hearing Scale (SSQ12-C)*

The secondary efficacy endpoint for the quality and speech understanding questionnaire will be based on subjects' responses on the SSQ12-C as recorded one month after crossover from the first strategy to the second strategy. The SSQ12-C is a comparative, closed-ended questionnaire composed of 12 items assessing speech perception, spatial hearing, sound quality, and listening effort. A response of 0 on the questionnaire indicates equivalent performance between FAST and ACE, while positive or negative responses indicate a preference for one strategy over the other.

The difference between the two study groups will be evaluated with a two-sided t-test using average responses on the SSQ12-C across the 12 questions within each group. Success for this secondary endpoint will be based on a non-significant result, indicating no difference between the two groups in terms of crossing over from one strategy to the other (i.e., not rejecting the null hypothesis that responses from the two groups are equivalent). The mathematical expressions are:

$$H_0: \mu_{G1} = \mu_{G2},$$

$$H_a: \mu_{G1} \neq \mu_{G2},$$

where:

μ_{G1} = mean response value on the SSQ12-C for Group 1;

μ_{G2} = mean response value on the SSQ12-C for Group 2.

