1.0 Introduction

The Fundamental Asynchronous Stimulus Timing (FAST) strategy offers excellent potential as a low power alternative coding strategy to the current default strategy in Nucleus® cochlear implants, Advanced Combination Encoder (ACE). Additionally, FAST offers potential bilateral benefits – localization and listening in spatially separated noise – because it has been shown in acute, controlled studies to provide more access to interaural timing difference (ITD) cues (Smith, 2010). FAST outputs a pulse at a time and level that corresponds with the exact time and amplitude of the peak of each envelope cycle. In contrast, ACE uses a fixed pulse rate (default of 900 pulses per second per channel) that bears no relationship to the coded acoustic stimulus.

Previous research with experienced cochlear-implant recipients has shown issues with conversion from ACE to FAST. The FAST strategy typically sounds very different in quality, and acclimatization can be lengthy. This extended adaptation time makes it difficult to show conclusively that FAST is non-inferior to ACE for speech understanding. A potential barrier to evaluating performance with FAST in current cochlear-implant recipients is the extensive amount of prior experience that many recipients have using ACE. Hence, there is a distinct need to evaluate FAST in newly implanted recipients.

The present study will compare speech intelligibility and sound quality with FAST and ACE in a group of 20 newly implanted subjects. There will be a 3-month period of take-home experience with each strategy in a crossover design. The battery life benefit of FAST compared to ACE will also be quantified.

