3.2 Sound Processor Description

Commercially available Nucleus 5 (CP810) sound processors will be used in this IDE. There have been no changes to the hardware of the CP810 processor. The CP810 is a behind-the-ear (BTE) sound processor. It is functionally similar to the newer generation Nucleus 6 (CP900 series) and Nucleus 7 (CP1000) processors, but without some of the advanced features (i.e. SmartSound iQ, Wireless Accessories, Data Logging, and iPhone compatibility). The CP810 processor will be loaded with different firmware for the ACE and FAST portions of the crossover study.

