9.2 Risks

With any cochlear implant program, there is a very small risk of unintentional over-stimulation. Subjects may experience sounds in mapping that are uncomfortably loud.

There is a risk that recipients may experience difficulty converting from the initial strategy to the crossover strategy. It is known from previous studies with experienced cochlear implant recipients that the experimental FAST strategy can sound very different in quality to the default ACE strategy. Some experienced ACE recipients have struggled to adapt to the FAST strategy over an 18-week period. The conversion risk is clearly identified in the patient informed consent form. The consent form also clearly indicates the option to withdraw from the study at any time.

Subjects will not be able to use their personal sound processor until the completion of the study. Instead, they will be loaned the CP810 sound processor for the duration of their participation. The CP810 processor has been shown to have similar general performance outcomes to the Nucleus 6, Kanso, and Nucleus 7 sound processors. However, during study participation, subjects will not have access to some advanced features (adaptive directionality, SmartSound iQ, wireless accessories, and iPhone compatibility). These differences are clearly explained in the patient informed consent form. At the end of the trial, subjects will be fit with their personal sound processor and will have access to the full range of features that are commercially available at that time.

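### Battery logs may end at switch-off yet are analysed as battery life, so the reported FAST gain can be too small (Protocol 5.2.6, SAP 1.4.2.1)

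*Combined protocol and SAP*

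**What the plan says.** Under Protocol 5.2.6 each subject completes one questionnaire per strategy, with four logs in each. A log starts on a full charge, and its end is "what time the processor was turned off (or, if the battery ran out of power, what time this occurred". Switch-off is the ordinary end point and depletion the bracketed alternative. The section closes with "They will complete this process until they have gone through four cycles of fully charged batteries". That could mean using up each charge, but the text does not say so.

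SAP 1.4.2.1 states: "The secondary efficacy endpoint for battery life will be based on battery logs as recorded by the subject during the take-home period". It continues: "The estimated within-subject mean difference in battery life between FAST and ACE will be reported with a 95% confidence interval", and then "A one-sided t-test will be conducted at the 0.025 significance level". It does not say how a log that ended at switch-off is handled, nor how four logs become one value per strategy. The imputation models in SAP 1.9 are named for CNC score and average SRT only.

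Protocol 3.2 describes the CP810 as "without some of the advanced features (i.e. SmartSound iQ, Wireless Accessories, Data Logging, and iPhone compatibility", so the documents offer no device record against which to check the diary.

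**The concern.** A log that ends because the subject switched off shows only that the battery lasted at least that long. In survival terms it is right-censored. Entered as a battery life, it records wear time. The strategy with the longer life has more of its logs cut short, so a real advantage for FAST shrinks, and it shrinks most when the advantage is largest.

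Quantifying the battery benefit is the first secondary objective (Protocol 2.0), so the estimate and its interval matter as well as the test. If the reason a log ended is not captured at the time, it may not be recoverable later.

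**Working it through.** **Plan's own figure.** There is none for this endpoint. The sample sizes of 8 and 11 in SAP 1.2 concern CNC and BKB only.

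**Inputs from the documents.** 20 subjects, 4 logs per strategy, within-subject FAST - ACE difference, one-sided 0.025.

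**Assumed inputs.** Mean battery life m and mean daily wear w as listed below. Between-subject SD is 1.0 h for life and 1.0 h for wear, and log-to-log SD is 1.5 h for each. All distributions are normal, wear is the same on both strategies, and the four logs are averaged.

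**Model.** Recorded time = min(battery life, wear). For normal variables

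E[recorded] = m·Φ(d) + w·Φ(−d) − θ·φ(d), with d = (w − m)/θ and θ = √(1.0² + 1.0² + 1.5² + 1.5²) = √6.5 = 2.55 h.

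The expected share of logs ending at switch-off is Φ(−d).

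**Worked case: ACE 10 h, FAST 14 h, wear 14 h.**
- ACE: d = 4/2.55 = 1.569, Φ = 0.9417, φ = 0.1165. Expected log = 10 × 0.9417 + 14 × 0.0583 − 2.55 × 0.1165 = 9.936 h.
- FAST: d = 0. Expected log = 14 − 2.55 × 0.3989 = 12.983 h.
- Expected gain = 12.983 − 9.936 = 3.05 h, against a true 4 h.

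The same formula gives the other rows. Coverage comes from simulating 20,000 trials with the paired t interval.

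| ACE / FAST / wear (h) | Mean ACE log | Mean FAST log | Estimated gain | True gain | FAST logs ended at switch-off | 95% CI coverage |
|---|---|---|---|---|---|---|
| 6 / 9 / 14 | 5.999 | 8.976 | 2.98 | 3 | 2% | 95% |
| 10 / 14 / 14 | 9.936 | 12.983 | 3.05 | 4 | 50% | 6% |
| 12 / 18 / 14 | 11.685 | 13.936 | 2.25 | 6 | 94% | 0% |

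**Test.** With equal wear and no true difference, both means are cut by the same amount. The expected difference is 0 and simulated rejection stays at 2.5%. Power suffers only in extreme cases: at 16/24/14 h the estimate is about 0.31 of 8 h and power about 23%. In the three tabled cases power is essentially 100%.

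**Sensitivity to the SDs.** With between-subject/log SDs of 0.5/1.0 h and 1.5/2.5 h, the 12/18/14 case gives 2.07 and 2.47 of 6 h, with coverage 0% in both.

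**Dropping switch-off logs is no remedy.** A separate check used between-subject SD 2 h, log SD 1.5 h and wear SD 2 h, with ACE life 14 h, FAST life 18 h and wear 14 h. The true gain of 4 h became 1.12 h with the mean of four logs. It became 3.09 h with run-out logs only, and 71% of subjects then had no usable pair.

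**The case against.** The strongest reply is that the problem may not exist in practice. Protocol 5.5.3 says instructions come with the questionnaire at Visit 4. Neither the instructions nor the form is in the documents; they may require run-out or already record how a log ended. The phrase about four cycles can be read the same way. And if batteries run out well within a day's wear, as in the first row of the table, nothing material is lost. All of this stands, and it limits the point to the wording of the two sections.

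A second reply is that the bias works against FAST, so a positive test remains credible. That also stands. It does not repair the estimate or its CI, which the objective asks for.

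A reader might go further and infer a risk of falsely declaring FAST superior. The arithmetic allows it: with a true life of 16 h on both strategies and wear of 14 h on ACE but 15 h on FAST, the model gives a spurious +0.72 h and 89% rejection. But that needs longer wear on FAST, and battery life near or beyond the wear day. At a life of 8 h the same shift leaves rejection at 2.6%. The 89% also assumes that each subject's wear shifts by the same amount; letting it vary by subject and strategy with SD 0.7, 1.0 or 1.5 h lowers it to about 70%, 56% or 36%. Nothing in the documents suggests longer wear on FAST. Order is randomised and subjects are blinded (Protocol 5.1). Protocol 1.0 says "The FAST strategy typically sounds very different in quality, and acclimatization can be lengthy" and Protocol 9.2 adds "Some experienced ACE recipients have struggled to adapt to the FAST strategy over an 18-week period". If these bear on wear at all, they point to less wear on FAST, which again works against FAST. They also concern experienced recipients and give no wear data.

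**Conclusion.** The point holds as an attenuation problem. As worded, the two sections let wear time be analysed as battery life. With similar wear and a truly longer FAST life, the reported gain is too small and its 95% CI can miss the true gain, while the superiority test keeps its error rate and may lose power. The size cannot be derived from the documents. Over the tabled scenarios it runs from negligible (2.98 of 3 h) to severe (2.25 of 6 h), depending on how battery life compares with the wear day. A false positive is possible in principle but unsupported.

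The missing rule for combining four logs is by itself only an unstated detail; it matters here because the choice changes how far the estimate is distorted. Study success rests on CNC and BKB alone (SAP 1.4.1, 1.5), so this is worth fixing but does not threaten the trial's main conclusion.

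**What to change.** **Protocol 5.2.6.** Have each log cover one full charge. Subjects record every on and off time until the battery runs out, where practical without recharging in between. Battery life is the summed on-time, so that hours switched off do not count. Add a tick-box for how the log ended: ran out, or switched off or recharged first. If the unseen form already does this, only the protocol text needs aligning.

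**SAP 1.4.2.1.**
1. Use the mean of the four logs per subject and strategy.
2. Report the share of logs not run out, by strategy.
3. State that, if this share is material and wear is similar, the estimated gain is likely an underestimate.
4. Keep the planned t-test. Optionally add a supportive analysis that treats logs not run out as right-censored, for example a Tobit or accelerated-failure-time model with strategy, period and a random subject effect.

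**Cost.** One diary instruction, one tick-box and a short SAP paragraph. The diary becomes slightly longer, and following a charge over more than one day is some burden. Any censored model depends on its assumed distribution and on switch-off being unrelated to the charge left. It helps little if almost no FAST log runs out, so the diary change matters more than the model.

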5.2.7 Quality and Speech Understanding Questionnaire

The comparative version of the Speech, Spatial and Qualities of Hearing scale (short form), the SSQ12-C (Noble et al., 2013), will be administered at 4-months post IA (1 month post-crossover). This scale is a 12-item questionnaire that records a subject's experiences in the areas of speech perception, spatial hearing, sound quality, and listening effort.

5.3 Preoperative Procedures

5.3.1 Visit 1

Visit 1 will take place at the Clinical Sites. A candidacy evaluation will be conducted to determine the subject's eligibility to enroll in the study. The candidacy evaluation will include a hearing history, air conduction and bone conduction audiogram, a CNC word test, and an AzBio sentence test.

5.4 Surgical Procedure

There are no modifications to the standard surgical procedure for this study.

5.5 Postoperative Procedures

5.5.1 Visit 2

Visit 2 will be conducted at the Clinical Sites. Procedures will include initial activation and mapping of the first strategy (Group 1 will receive FAST, and Group 2 will receive ACE). Subjects will be oriented to use of the CP810 processor.

5.5.2 Visit 3

Visit 3 will be conducted at the Clinical Sites. Procedures will include fine-tuning of the initial strategy.

5.5.3 Visit 4

Visit 4 will be conducted at the Clinical Sites. The first battery life questionnaire will be handed out to the subject, and instructions for completing and returning

CONFIDENTIAL

the questionnaire will be provided. Mapping will be conducted for fine-tuning of the initial strategy.

5.5.4 Visit 5

Visit 5 will include endpoint speech perception tests, the Reading Span Test, clinical audiological testing, and programming of the crossover strategy. Depending on the Clinical Site, endpoint speech testing (CNC words and BKB sentences) and the Reading Span Test will be conducted either at the Clinical Site or at the Denver Research & Technology Labs (Cochlear Americas). All programming will be conducted at the Clinical Sites. Since endpoint speech testing will be administered by a clinician blinded to the current treatment, endpoint speech testing and programming will be performed by different clinicians. The crossover strategy will be programmed (Group 1 will receive ACE, and Group 2 will receive FAST), and the acute sound quality ratings will be conducted.

5.5.5 Visit 6

Visit 6 will be conducted at the Clinical Sites. Procedures will include fine-tuning of the crossover strategy.

5.5.6 Visit 7

Visit 7 will be conducted at the Clinical Sites. The SSQ12-C will be completed, and the second battery life questionnaire will be handed out to the subject. Mapping will be conducted for fine-tuning of the crossover strategy.

5.5.7 Visit 8

Visit 8 will include endpoint speech perception tests, clinical audiological testing, final programming, and fitting with the patient's personal sound processor. Depending on the Clinical Site, endpoint speech testing will be conducted either at the Clinical Site or at the Denver Research & Technology Labs (Cochlear Americas). All programming will be conducted at the Clinical Sites. Since endpoint speech testing will be administered by a clinician blinded to the current treatment, endpoint speech testing and programming will be performed by different clinicians. The subject will be fitted with his or her personal sound processor and the ACE strategy (both groups). Counseling on use of the personal sound processor will be provided.

CONFIDENTIAL

5.6 Summary of Data Collection Visits

Testing at Clinical Sites								
	Visit 1	Visit 2	Visit 3	Visit 4	Visit 5	Visit 6	Visit 7	Visit 8
Test	Candidacy	Initial Activation (IA)	1 week (post IA)	1M (post IA)	3M (post IA)	3M plus 1 week (post IA)	4M (post IA)	6M (post IA)
Strategy Programming		Program initial strategy Group 1 - FAST Group 2 - ACE	Fine-tuning of initial strategy	Fine-tuning of initial strategy	Program crossover strategy Group 1 - ACE Group 2 - FAST	Fine-tuning of crossover strategy	Fine-tuning of crossover strategy	Program ACE; counsel use of personal processor (both groups)
Clinical Audiological Testing	X				X			X
Sound Quality Ratings					X			
Battery Life Questionnaire				X			X	
Quality and Speech Understanding Questionnaire							X	

Testing either at Clinical Sites or at Denver Research & Technology Labs (Cochlear Americas)								
	Visit 1	Visit 2	Visit 3	Visit 4	Visit 5	Visit 6	Visit 7	Visit 8
Test	Candidacy	Initial Activation (IA)	1 week (post IA)	1M (post IA)	3M (post IA)	3M plus 1 week (post IA)	4M (post IA)	6M (post IA)
Speech Perception					X			X
Reading Span Test					X			

Table 1. Summary of data collection visits.

6.0 Adverse Events

An adverse event (AE) is any undesirable clinical or medical occurrence associated with the use of the device, procedure, or participation in the study, which does not result in serious injury or illness related to the surgical procedure or the device.

A serious adverse event (SAE) is any untoward medical occurrence that

- results in death
- is life-threatening

CONFIDENTIAL

- requires inpatient hospitalization or prolongation of existing hospitalization
- results in persistent or significant disability/incapacity
- requires medical or surgical intervention to prevent life-threatening illness or injury or permanent impairment to a body structure or a body function
- leads to fetal distress, death, or congenital abnormality or birth defect
- is a medically important event or reaction

6.1 Assessment and Reporting of Adverse Events

To monitor subject safety throughout this IDE study, any procedure or device related adverse events will be recorded. Information on all adverse events will be maintained by event type. The investigator will complete an Adverse Event form if any adverse event is reported or observed for a subject during this IDE, even if the event was acknowledged as a risk factor in the Informed Consent form.

Adverse device effects refer to any undesirable clinical or medical occurrence associated with use of the device or participation in the study. Any/all adverse device effects are to be recorded via the Adverse Event form. Adverse device effects will be reported if observed, even if they were acknowledged as risk factors in the Informed Consent form.

6.2 Unanticipated Adverse Device Effects

Unanticipated adverse device effects refer to any event not identified above that represents a “serious adverse effect on health or safety or any life-threatening problem or death caused by, or associated with, a device if that effect, problem or death was not previously identified in nature, severity, or degree of incidence in the investigational plan or application, or any other unanticipated serious problem associated with a device that relates to the rights, safety, or welfare of subjects.” [FDA 21 CFR 812.3(s)]

Investigators are to inform their respective Institutional Review Boards (IRBs) and Cochlear Americas immediately if an unanticipated adverse device effect is suspected (no more than 10 working days after the investigator learns of the effect). If the case is determined to be an unanticipated adverse device effect, the investigator will fill out an “Unanticipated Adverse Device Effect Form.” Cochlear Americas will report the results of an evaluation of the unanticipated adverse device effect to the FDA and all other reviewing IRBs and investigators within 10 working days after first receiving notice of the event.

CONFIDENTIAL

